6.4. Inclusion of Women and Minorities

Every attempt will be made to include all genders and minorities that present with pulmonary fibrosis and are not exempted due to exclusion criteria.

7. Study Design

Assignment of Subject Number and Randomization

This is a randomized placebo-controlled double-blinded trial. Upon enrollment, each subject will be sequentially issued a unique subject number starting at 100. Once a number has been assigned to a subject, it cannot be re-assigned to another subject. Subjects will be encouraged to complete the study, although they may withdraw at any time without prejudice. Termination will be reported to the sponsor in a timely manner. Details of the reason(s) why a subject was dropped or withdrew from the study will be documented. Enrollment will continue until the number of subjects specified in the protocol has been attained. The data from all subjects that have been given a study compound will be retained for analysis.

8. Randomization

The subjects will be randomized to the placebo control or N115 drug study groups using a random number set.

9. Telephone Communication

Subjects will be instructed to call the clinic should they be experiencing any self-perceived adverse events, or if they have any study-related questions. All telephone information will be documented.

10. Products Description (How Administered)

The product is an all-natural patented 0.2% sodium pyruvate in 0.9% sodium chloride nasal spray solution, pH 7.2, with 0.02% benzalkonium chloride as a preservative. The patient will be instructed on the use of the nasal spray prior to the start of the clinical trial. The plastic bottle contains 30 mL. It is non-steroidal. Patients will forcibly expel air from their lungs and then will administer 3 sprays per nostril while inhaling strongly so that the drug is transported through the nose and into the lungs. The drug is to be administered 3 times per day (morning, mid-day, and evening). The product comes with instructions for administration (3 sprays per nostril).

11. Concomitant Therapy

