13.2. Safety Testing

- Physical Exam
- Vital Signs
- Weight
- Blood pressure
- Pulse
- Temperature
- Blood analysis
- Complete blood count (CBC)
- Clinical tests, including:
 - Urea nitrogen: serum creatinine: total protein: serum albumin: total globulin: albumin/globulin ratio: total bilirubin: alkaline phosphatase: aspartate aminotransferase (AST or SGOT): alanine aminotransferase (ALT or SGPT): LDH: GGT: serum sodium: potassium: chloride serum: carbon dioxide: total cholesterol:hdl ratio:
- Urine test for women of child-bearing age

- Efficacy tests
 - o Nasal examinations by a rhinoscope fitted with a camera
 - \circ FEV₁, FVC

14. Withdrawal Criteria

The patients can withdraw from the study at any time, and for any reason. All data collected from these patients will be analyzed. Reasons for withdrawal will be recorded to insure that it was not due to an adverse event.

The subject has the right to withdraw from the study at any time.

The subject will be withdrawn from the study if:

- There is deterioration in the subject's signs and symptoms and/or the subject develops a disease or condition that, in the opinion of the investigator, would compromise the subject's safety by continuing in the study.
- In the investigator's judgment, it is in the best interest of the subject.
- There is a violation of the protocol inclusion and/or exclusion criteria, as deemed relevant by the investigator and discussed with the medical monitor.
- The subject begins to take any medication(s) that is(are) excluded by the protocol.
- Any of the conditions for stopping rules are met.

If a subject withdraws prematurely from the study due to the above criteria or any other reason, study staff should make every effort (at withdrawal) to complete the full set of evaluations listed for the early termination/end-of-study visit. The reason for subject withdrawal must be documented in the case report form (CRF).

If a subject withdraws from the study due to an adverse event (AE) (eg, clinical signs, symptoms, or clinically significant laboratory abnormality), the subject will be asked to return to the clinic, at a minimum, for the evaluations scheduled for the posttreatment follow-up period. If the AE has still not resolved, additional follow-up will be performed, as appropriate, and documented in the subject's medical records. As a minimum requirement, AEs should be followed for 30 days after the subject's last dose of study medication.

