In the case of a subject lost to follow-up, attempts to contact the subject must be made and documented in the subject's medical records.

Withdrawn subjects will not be replaced.

15. A Description of Clinical Procedures, Laboratory Tests, or Other Measures to be Taken to Monitor the Effects of the Drug in Human Subjects and to Minimize Risk

Tests and analyses will be conducted 3 times during the study. If any aberrant values occur, the principal investigator will determine if that patient should continue in the study or be removed. All aberrant values that occur during the study will be considered adverse events. A summary of possible risks will be provided to the patients. Previous risks of using the product are minimal, which included irritation to the nose cavity reported by 1 patient out of 1,869.

16. Safety Precautions Included in this Study

The 0.2% nasal sodium pyruvate inhalation has been administered to both healthy humans and humans with lung diseases, without the occurrence of any SAE.

- First administration of nasal spray on the premises of a hospital/clinic.
- The initial nasal spray will be administered under the supervision of medical staff.
- If a subject develops any adverse event during the follow-up period after study drug administration, the subject will be treated to a satisfactory resolution before being discharged from the clinic.
- Subjects will remain at the test site for monitoring for 30 minutes after the initial inhalation of the nasal spray.
- Follow up telephone communications, as needed.

17. Product Evaluation Questionnaire

This self-administered questionnaire measures the patients' impressions of how the drug affected their nasal cavity, their coughing, and their breathing. It is designed to evaluate changes in a subject's quality of life over time. It will be administered during all clinic visits.

18. Daily Data Logbook

Subjects will use this diary card to record the number of their coughs per day, any self-perceived adverse events, and any medication changes during the study.

19. Urinalysis

Samples will be taken and analyzed to determine if any child-bearing females are pregnant.

20. Study Management

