20.2. Data Collection, Management, and Statistical Analysis

The data management staff at the research clinic will collect and manage the data. Data will be obtained, maintained, and transmitted securely in accordance with HIPAA guidelines. Monitoring and auditing of the data will be conducted by a staff member of Cellular Sciences.

Statistical analysis will be performed on deidentified data. The basic statistical analysis will be repeated measurements of Analysis of Variance using baseline measurements as a covariant (ANCOVA). Age, sex, time since initial diagnosis with IPF, concurrent medications and smoking status are considered potential covariates. Number of coughing episodes reported for a 24-hour pre-study period, and other pre-study data information, will be compared to the data collected during the trial. The differences between baseline data and the data collected during the trial will be compared and analyzed (Within treatment). Additionally, the data of the patients on the experimental therapy will be compared to the data generated by the patients on placebo (Between treatments). P values of <0.5 will be considered significant. FEV1 and FVC will similarly be analyzed as secondary outcome measurements. Relative changes will be analyzed by JMP, Matillion, XLSTAT or R software by [name] or [name], who will be responsible for the statistical analysis.

Partial patient data will be included in the statistical analysis if patients withdraw from the study, but data from non-compliant patients will be excluded. Our previous research (REF) indicates that a sample size of 20 is sufficient to detect a statistically significant difference (p<0.05) between treatment groups. We have chosen to enroll 25 patients in each treatment group to ensure we achieve the necessary sample size, taking into account that some patients may not complete the study, and some data will be incomplete or excluded from the study.

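### Section 20.2 names a repeated-measures ANOVA without saying how incomplete patients are kept, and names no primary between-group contrast for cough

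*Combined protocol and SAP*

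**What the plan says.** The analysis text is one short part of section 20.2: "The basic statistical analysis will be repeated measurements of Analysis of Variance using baseline measurements as a covariant (ANCOVA"), followed by a list of potential covariates. Comparisons are described as within treatment (baseline against on-trial data) and between treatments (N115 against placebo). No day, average or interaction is attached to either. Section 2.1 sets a 25% reduction in coughing episodes, without saying against what or when.

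On incomplete patients, the intent is to keep data:

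- Section 20.2: "Partial patient data will be included in the statistical analysis if patients withdraw from the study".
- Section 14: for patients who withdraw, "All data collected from these patients will be analyzed".
- Section 7: "The data from all subjects that have been given a study compound will be retained for analysis".
- Section 20.3: data collected up to withdrawal stay in the database.

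The one stated exclusion, in section 20.2, concerns non-compliance: "but data from non-compliant patients will be excluded". Section 14 adds that "Withdrawn subjects will not be replaced", and section 20.2 expects that "some patients may not complete the study, and some data will be incomplete or excluded from the study".

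FEV1 and FVC are measured on day 1 and at clinic visits on days 8, 14 and 22. Coughs are logged daily. Section 5.2 runs the log for 21 days; the footnote to the section 13.1 schedule ends it at day 14.

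**The concern.** There are two gaps, both in the primary analysis.

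First, classical repeated-measures ANOVA needs a complete row for each patient, so someone who misses one repeated measurement contributes nothing. The plan promises to use partial data but does not name a method that does so. Section 20.2 lists four software packages and fixes no model, so the choice between a complete-case fit and an all-data fit could be made after the data are seen. A complete-case fit loses power. It is also biased if leaving the trial is related to cough.

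Second, with a daily diary and three post-baseline clinic visits, several between-group results could later be presented as the primary one. Unless one is named in advance, the nominal 5% error rate is not protected.

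**Working it through.** **1. The plan's own figure.** Section 20.2 says 20 patients suffice at p<0.05 and enrols 25 per group. No effect size, SD, power or sidedness is given, so the 20 cannot be reproduced. If 20 means per group, 20/(1 − 0.20) = 25, which fits an unstated 20% loss. At two-sided 0.05 and 80% power, 20 per arm corresponds to a standardised difference of (1.960 + 0.842) × √(2/20) = 0.886.

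**2. How quickly complete-case analysis uses up the margin.** Assume three repeated measurements, each missing independently with probability m. Complete cases per arm = 25 × (1 − m)³, and power = Φ(0.886 × √(n/2) − 1.96). The last column is the effective number per arm for the visit-averaged contrast when all available data are used by likelihood, with compound symmetry and correlation 0.5 to 0.7.

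| m per measurement | Complete cases per arm | Power, complete cases | Effective n per arm, all data |
|---|---|---|---|
| 5% | 21.4 | 82.7% | 24.6-24.8 |
| 7.2% | 20.0 | 80.0% | 24.4-24.6 |
| 10% | 18.2 | 76.3% | 24.1-24.5 |
| 15% | 15.4 | 69.0% | 23.5-24.2 |

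So about 7% missing per measurement would use the whole margin between 20 and 25. At 10%, the complete-case analysis falls below the plan's own 20.

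**3. Power for a 25% reduction.** Assumed inputs: residual log SD 0.45, correlation 0.6 between three periods, 20% monotone dropout spread evenly over them.

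- Effect on the log scale: ln(0.75) = −0.288.
- SD of the three-period average: 0.45 × √((1 + 2 × 0.6)/3) = 0.385.
- Standardised effect: 0.288/0.385 = 0.747.
- Completers, 25 × 0.8 = 20 per arm: t-based power 63% (64% by simulation).
- All data, effective 22.5-22.9 per arm (correlation 0.5-0.7): t-based power about 69%. Simulation gave 70-72%; the upper end is slightly optimistic because the covariance was treated as known.
- No missing data, 25 per arm: 73%.

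**4. If high coughers leave.** With the same inputs and dropout made to depend on cough severity, simulated power is 52-58% for completers and 70-71% with all data. The completers' estimate falls from 25% to about 21-23%; the all-data estimate stays near 25%.

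**5. No named contrast.** Suppose success could be claimed at whichever of three time points is best, each tested two-sided at 0.05. The chance that at least one of three correlated z-statistics exceeds 1.96 in absolute value is 12.5%, 10.9% and 9.8% at correlation 0.5, 0.7 and 0.8. One pre-named contrast keeps it at 5%.

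**The case against.** The strongest reply is that the plan nowhere says incomplete patients are dropped. Its statements on withdrawals point the other way, and JMP and R, both listed, can fit a mixed model that might loosely be called repeated-measures ANCOVA. That is correct. A reader might infer that the plan deletes anyone with a missing visit, but it states no complete-case rule. What remains is that the named method in its classical form would do this, and nothing in the text excludes that form.

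A reader might also infer that the analysis yields three visit tests, any of which could count. The documents do not say so either. Repeated-measures ANOVA ordinarily gives a treatment main effect and a treatment-by-time interaction, with visit tests as follow-up. The 10-12% is therefore a worst case. Days 8, 14 and 22 are also clinic visits, which suit FEV1 and FVC; cough is a daily diary, and the plan does not say how its days become repeated measurements. This makes the missing contrast less settled.

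The 20% loss is inferred from 20 and 25, not stated, and the SD, correlation and dropout patterns are assumed. On a t-based calculation the power gain is about 6 points rather than 8, before the cost of estimating the covariance. The bias is small, and needs dropout related to cough within 21 days.

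**Conclusion.** The point holds as a gap in specification, not as a proven contradiction. Two things are firm from the text alone: the named method is not tied to any way of keeping incomplete patients, although the plan says their data will be used; and no primary between-group contrast for cough is named.

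The size is illustrative. Under the assumptions shown, a complete-case fit costs roughly 6 to 8 points of power at 20% incomplete, and more if high coughers leave, when its estimate also shrinks by about 2 to 4 percentage points. The worst-case error from a free choice among three time points is about 10-12%. The all-data advantage on bias requires that dropout depend on cough values already observed. The change should be made before unblinding; it costs little and removes a choice that could otherwise be made with the results in view.

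**What to change.** In section 20.2, replace the repeated-measures ANOVA with a likelihood-based mixed model for repeated measures on all available data: treatment, period, treatment-by-period and baseline, with the covariance structure stated. An unstructured covariance is one acceptable choice. Define how daily cough entries are summarised into fixed periods, for example weekly means. Name one primary between-group contrast, for example the average N115-minus-placebo difference over the on-treatment period. Label other time points and within-group changes as supportive, and add a sensitivity analysis for missing data.

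Before the contrast is fixed, sections 5.2 and 13.1 must be reconciled on how long the diary runs, since this decides which periods exist.

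The model and contrast need SAP wording only: no extra patients, visits or procedures. JMP and R, already listed, can fit the model.

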5.1. Pre-study

Individuals with a clinical diagnosis of idiopathic pulmonary fibrosis (as defined by the WHO and the Thoracic Society) will be solicited for participation in this phase 3 trial. After signing the informed consent, participants will be randomly assigned to either the placebo or drug groups in a double-blinded randomized fashion. On pre-study day 1 (Screening Visit), and, after signing the informed consent, they will have their degree of nasal inflammation and erythema, nasal cellular morphology, SaO₂, and FEV₁, and FVC levels recorded (baseline). All subjects will have a blood sample taken, and women of child-bearing age will provide a urine sample. The subjects will fill out a quality of life questionnaire (chronic respiratory disease questionnaire (CRDQ), and they will be given a data logbook in which they will record the number of coughs they experience each day for 7 days until they return to the clinic to begin the study (baseline). Any subject who is not compliant $\geq 80\%$ will not be entered into the trial.

Blood will be analyzed for CBCs, and for standard clinical variables, including urea nitrogen, serum creatinine, total protein, serum albumin, total globulin, albumin/globulin ratio, total bilirubin, alkaline phosphatase, aspartate aminotransferase (AST or SGOT), Alanine Aminotransferase (ALT or SGPT), Lactate Dehydrogenase (LDH), Gamma-glutamyl Transferase (GGT), Serum Sodium, Potassium, Chloride Serum, Carbon Dioxide, C-reactive protein, and Total Cholesterol:HDL Ratio to determine organ health. Subjects may not enter the study until the blood and urine samples are analyzed and evaluated to confirm that subjects do not have a metabolic abnormality that would prevent entry, and that women are not pregnant.

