5.2. Study Days

Following the 7-day pre-study period, which includes time for analysis of the blood and urine, eligible IPF patients will return to the clinic and be admitted to the 21-day study. On the first day of the study, these patients will have a physical exam and their vital signs will be recorded. Then, their degree of nasal inflammation and erythema will be evaluated and recorded as before, as will their SaO2, FEV1 and FVC levels and frequency of coughing. Patients will be instructed on how to self-administer their first dose of the nasal spray drug (0.2% sodium pyruvate in 0.9% sodium chloride solution) by first forcefully expelling air from their lungs, and

then spraying 3 squirts of the drug into each nostril, and then forcefully inhaling the drug so that the drug is inhaled into the lungs. After 1 hour, the subjects will have their vital signs taken again. Efficacy and safety evaluations will occur at this 1-hour time period, too, and then again at 2 and 3 hours. The subjects will fill out the product evaluation questionnaire, be given a daily data log form and be given enough drug to last for 21 days (3 bottles), and released from the clinic.

For the next 21 days, subjects will self-administer 3 squirts per nostril of the nasal spray, as instructed, 3 times daily; upon wakening, noon/midday, and before bedtime, Additionally, they will fill out the Daily Data Log form each day to record the number of daily coughs. Patients will be contacted by phone every 2 days to review symptoms and protocol compliance.

On days 8, 14 and 22, they will return to the clinic and have their blood analyzed, vital signs taken, and their degree of nasal inflammation, erythema and cellular morphology recorded. As before, they will be tested for FEV_1 , FVC and SaO_2 levels. The number of coughs they experienced and other information will be discussed with the clinician. They will fill out the product evaluation questionnaire and the CRDQ, and they will then be released from the study on day 22. These data will then be evaluated.

6. Criteria for Patient Selection, Exclusion of Patients, and Number of Patients 6.1. Subject Selection and Number of Patients to be Studied

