24.2. Examples of Adverse Events

- Inter-current illnesses
- Injuries
- New symptomatology (this does not include symptoms expected as a result of the subject's condition unless it is beyond what is normally expected)
- Significant laboratory abnormalities
- New abnormal physical exam findings
- Significant exacerbation of pre-existing conditions
- Death
- A life-threatening event
- In-patient hospitalization (not required as part of the treatment) or prolongation of existing hospitalization
- Disability or permanent damage
- A congenital anomaly/birth defect
- Cancer
- Drug overdose

24.3. Recording and Documentation of Adverse Events

Any adverse event (i.e., a new adverse event or an exacerbation of a pre-existing condition) with an onset date after study enrollment should be recorded as an adverse event on the CRF. All adverse events must be recorded on the appropriate CRF regardless of the severity or relationship to study medication. An adverse event or laboratory abnormality with an onset date before study enrollment is considered to be pre-existing in nature. These pre-existing events will be noted in the CRFs.

All SAEs occurring during this study, whether observed by the physician, nurse, or reported by the patient, will be recorded on the Florida Advanced Medical Research Adverse Events form.

24.3.1 Investigator Report of a "Serious Adverse Event" to Cellular Sciences.

Cellular Sciences (Sponsor) must be notified regarding the occurrence of any SAE that occurs after enrollment in the study protocol, regardless of the causal assessment to study medication. The procedures for reporting SAEs are as follows:

- Complete the "Serious Adverse Event Report."
- Email the SAE Report to Cellular Sciences (see below) within 24 hours of the investigator's knowledge of the event.
- These preliminary reports must be followed by detailed descriptions that include copies of hospital case reports, autopsy reports, and other documents when requested and applicable. Cellular Sciences may request additional information from the Investigator to ensure the timely completion of accurate safety reports.

The contact information for reporting SAEs is as follows:

[name].	[name].
Director	Director
Cellular Sciences	Cellular Sciences
[name]	[name]
[name]	[name]
[contact]	[contact]

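### Section 20.2 excludes undefined non-compliant patients after randomisation and sits badly with Section 7; the main analyses should keep every dosed patient as randomised

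*Combined protocol and SAP*

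**What the plan says.** The rule is in Section 20.2: "Partial patient data will be included in the statistical analysis if patients withdraw from the study, but data from non-compliant patients will be excluded". The section gives no criterion for non-compliance, does not say who decides or when, and does not limit the rule to any type of data. The analysis it describes is a baseline-adjusted repeated-measures comparison of cough, within and between treatments, with FEV1 and FVC handled in the same way.

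Other sections bear on the same patients:

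- Section 7: "The data from all subjects that have been given a study compound will be retained for analysis".
- Section 14, on patients who withdraw: "All data collected from these patients will be analyzed".
- Section 5.1 has the only numerical threshold. The sentence beginning "Any subject who is not compliant" sets 80% as a condition of entry after the seven-day pre-study period.
- Section 5.2, for the treatment period: "Patients will be contacted by phone every 2 days to review symptoms and protocol compliance". No cut-off is attached.
- Section 24.3, on safety recording: "All adverse events must be recorded on the appropriate CRF regardless of the severity or relationship to study medication". The diary in Section 18 also collects "any self-perceived adverse events, and any medication changes during the study".

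The available text defines no intention-to-treat, full-analysis, per-protocol or safety population.

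**The concern.** Compliance during treatment is observed after randomisation and can depend on how the patient is doing: whether the cough improves, or whether the spray is unpleasant. Removing patients on that basis means the arms compared are no longer the arms that were randomised. With no definition, the plan does not prevent the choice of whom to remove from being made once data are in hand. In a trial of 25 per arm, a few such choices can move the primary result.

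The rule also treats similar patients differently. One who stops the spray and withdraws is analysed; one who stops the spray but stays enrolled may be dropped.

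**Working it through.** **1. The rules side by side.** Take a patient who was randomised and dosed.

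| Patient | Section 7 | Section 14 | Section 20.2 |
|---|---|---|---|
| Withdraws | retained | analysed | partial data included |
| Stays enrolled, judged non-compliant | retained | not addressed | excluded |
| Withdrawn for starting a prohibited medication | retained | analysed | included as withdrawn, arguably excluded as non-compliant |

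No order of precedence is given. If retained in Section 7 means analysed, rows 2 and 3 conflict with Section 20.2. If it means only kept on file, Section 20.2 governs alone and the exclusion applies in full.

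**2. What the exclusion reaches.** Cough, FEV1 and FVC are named in Section 20.2. Nasal inflammation and erythema are listed among the efficacy observations in Section 13, and rhinoscopic examination among the efficacy tests in Section 13.2. So reading the exclusion as efficacy-only still takes in the nasal findings.

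**3. The plan's own allowance.** Section 20.2 states that 20 is sufficient (read here as per group) and enrols 25 per group to allow for incomplete or excluded data. The 20 cannot be reproduced, because no effect size, SD or power is given. The step to 25 fits an unstated 20% loss: 20 / (1 − 0.20) = 25. The plan thus leaves room for up to 25 − 20 = 5 patients per arm to be lost or excluded.

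**4. Illustration of the possible effect on efficacy.** Assumptions: no true effect, a normal outcome with SD 1, 25 per arm, a two-sample t-test at two-sided 0.05, 20,000 simulated trials, and the k worst-cough patients dropped from the active arm only. This is a simple stand-in for the planned ANCOVA, and the pattern of exclusion is deliberately extreme.

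| k dropped | Mean difference (SD units) | Chance of a false result favouring active |
|---|---|---|
| 0 | −0.004 | 2.6% (nominal 2.5%) |
| 2 | −0.154 | 8.8% |
| 3 | −0.217 | 13.0% |
| 5 | −0.337 | 23.4% |

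Dropping the same patients from placebo instead reverses the sign. Dropping them equally from both arms gives an expected difference of zero, by symmetry. The table therefore shows what the rule permits and does not forecast the bias.

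**5. Check on nasal irritation as the cause of non-compliance.** Section 15 gives 1 case in 1,869.

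- p = 1/1,869 = 0.0535%. Expected cases in 25 patients = 25p = 0.013.
- Chance of at least one = 1 − (1 − p)^25 = 1.3%.
- The exact 95% upper limit for 1/1,869 is 0.298%, which gives 1 − (1 − 0.00298)^25 = 7.2%.
- At assumed rates of 5% and 10%, the chance is 72% and 93%. The documents support neither rate.

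**The case against.** The strongest case on the other side has four parts.

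*The rule is about efficacy.* Section 20.2 describes only cough and lung function analyses, and no statistical analysis of adverse events is planned for the exclusion to distort. Adverse events are handled in Sections 15, 24.3 and 24.3.2, none of which carries a compliance condition. This largely stands. A reader might infer that the plan would hide adverse events or nasal irritation, and the documents do not support that. Collection and reporting are intact. The only named local risk is described as "Previous risks of using the product are minimal, which included irritation to the nose cavity reported by 1 patient out of 1,869", which makes even one case in an arm unlikely. Both arms also receive saline with the same 0.02% benzalkonium chloride (Section 3), so any loss may be similar in both. What remains is narrower: the exclusion reaches the nasal examination as a declared efficacy measure, and nothing exempts an adverse event summary if one is produced.

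*There is no proven contradiction.* The Section 7 sentence ends a paragraph on numbering and withdrawal, and may mean only that data are kept, as Section 20.3 says for withdrawn patients. This also stands. A reader might infer a flat contradiction, but the text shows an unresolved ambiguity. That does not remove the problem, because on the milder reading nothing limits Section 20.2.

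*Exclusions may be decided blind.* Patients and investigators are blinded, and compliance is reviewed every two days during treatment. So it is not established that exclusions would be chosen after seeing results by arm. But the plan does not say that they will be settled before unblinding. Blinded exclusion can still unbalance the arms if compliance depends on the treatment's effects.

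*A dose-count definition is not readily available.* The diary in Section 18 is not said to record doses taken. This stands, and the fix allows for it.

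**Conclusion.** The point holds as a defect in the analysis rule. As written, Section 20.2 removes randomised, dosed patients for undefined behaviour after randomisation, and no stated analysis population or precedence over Section 7 prevents it. The conclusion assumes that Section 20.2 is applied literally and that no population is defined in text not available for this review.

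The size and direction of any bias are unknown. The simulated figures depend on one-sided, outcome-related exclusion, and at most indicate that a handful of exclusions can matter with 25 per arm. The point does not rest on nasal irritation being common. It should be corrected before unblinding.

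**What to change.** Amend Section 20.2 to agree with Section 7:

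1. The main by-arm analyses of cough, FEV1, FVC and nasal examination include all randomised patients given at least one dose, in the arm to which they were randomised, whatever their compliance.
2. Adverse events are summarised for all dosed patients by treatment received.
3. The non-compliance exclusion is used only for a per-protocol sensitivity analysis of efficacy. Its criterion is fixed before unblinding and rests on data the trial already records, such as use of a prohibited medication or the compliance found at the two-day telephone reviews if that is documented. A criterion based on doses taken would need a dose record added to the diary.

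The cost is a few sentences, with no extra visits, tests or patients. The downside is that patients who missed doses may dilute the efficacy estimate. If k of 25 active patients gained no benefit at all, the average effect is multiplied by (25 − k)/25: 0.96 for one patient, 0.80 for five. The sensitivity analysis shows how much this matters. Slightly more minor nasal events may also be reported.
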